4.3.3 Additional Safety Assessments

4.3.3.1 Laboratory Data

Laboratory data will be summarized by treatment period, by treatment sequence and overall. Selected laboratory data will be graded according to NCI CTCAE v5.0 and will be summarized descriptively. Shift tables from baseline to worst post-baseline values will also be presented.

Potential Hy's law patients will be listed based on the laboratory data only: treatment-emergent elevated ALT or AST ($>3 \times$ baseline value) in combination with elevated total bilirubin ($>2 \times$ upper limit of normal [ULN]).

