 - Participants with documented liver metastases: AST and ALT $\leq 5 \times$ ULN
 - Participants with documented liver or bone metastases: ALP $\leq 5 \times$ ULN
- Total bilirubin $\leq 1.5 \times$ ULN with the following exception:
 - Participants with known Gilbert disease: total bilirubin $\leq 3 \times$ ULN
- Creatinine clearance ≥ 45 mL/min (calculated through use of the Cockcroft-Gault formula)
- Albumin ≥ 25 g/L (≥ 2.5 g/dL)
- For participants not receiving therapeutic anticoagulation: INR and aPTT $\leq 1.5 \times$ ULN
- For participants receiving therapeutic anticoagulation: stable anticoagulant regimen
- Intact normal skin without potentially obscuring tattoos, pigmentation, or lesions in the area for intended injection
- Negative HIV test at screening, with the following exception: participants with a positive HIV test at screening are eligible provided they are stable on anti-retroviral therapy, have a CD4 count $\geq 200/\mu\text{L}$, and have an undetectable viral load
- Negative hepatitis B surface antigen (HBsAg) test at screening
- Positive hepatitis B surface antibody (HBsAb) test at screening, or negative HBsAb at screening accompanied by either of the following:
 - Negative total hepatitis B core antibody (HBcAb)
 - Positive total HBcAb test followed by a negative (per local laboratory definition) hepatitis B virus (HBV) DNA test
 - The HBV DNA test must be performed for participants who have a negative HBsAg test, a negative HBsAb test, and a positive total HBcAb test.
- Negative hepatitis C virus (HCV) antibody test at screening, or positive HCV antibody test followed by a negative HCV RNA test at screening
 - The HCV RNA test must be performed for participants who have a positive HCV antibody test.
- If a port for IV delivery is present, acceptance to receive atezolizumab IV, and any other IV medication which may be required, through a peripheral line

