4.5.6 Laboratory, Biomarker, and Other Biological Samples

Samples for the following laboratory tests will be sent to the study site's local laboratory for analysis:

- Hematology: WBC count, RBC count, hemoglobin, hematocrit, platelet count, and differential count (neutrophils, eosinophils, basophils, monocytes, lymphocytes, other cells)
- Chemistry panel (serum or plasma): bicarbonate or total carbon dioxide (if considered standard of care for the region), sodium, potassium, chloride, glucose, BUN or urea, creatinine, total protein, albumin, phosphate, calcium, total bilirubin, ALP, ALT, AST, and LDH
- Coagulation: INR, and aPTT
- Thyroid function testing: thyroid-stimulating hormone, free T3 (or total T3 for sites where free T3 is not performed), and free T4
- HIV serology
- HBV serology: HBsAg, HBsAb, and total HBcAb for all participants; HBV DNA for participants with negative HBsAg and HBsAb tests and a positive total HBcAb test
- HCV serology: HCV antibody for all participants; HCV RNA for participants with a positive HCV antibody test
- Pregnancy test

All women of childbearing potential will have a serum pregnancy test performed at screening. Urine (or serum, if urine is not feasible) pregnancy tests will be performed at specified subsequent visits. If a urine pregnancy test is positive, it must be confirmed by a serum pregnancy test.

A woman is considered to be of childbearing potential if she is postmenarchal, has not reached a postmenopausal state (≥ 12 continuous months of amenorrhea with no identified cause other than menopause), and is not permanently infertile due to surgery (i.e., removal of ovaries, fallopian tubes,

and/or uterus) or another cause as determined by the investigator (e.g., Müllerian agenesis).

- Urinalysis (pH, specific gravity, glucose, protein, ketones, and blood); dipstick permitted

The following samples will be sent to one or several central laboratories or to the Sponsor or a designee for analysis:

- Serum samples for atezolizumab PK analysis through use of a validated assay
- Serum samples for assessment of ADAs to atezolizumab through use of a validated assay
- Archival or newly collected tumor tissue sample obtained at baseline for determination of PD-L1 expression and EGFR and/or ALK, if central testing is required

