5.3.5.7 Abnormal Liver Function Tests

The finding of an elevated ALT or AST ($>3\times$ baseline value) in combination with either an elevated total bilirubin ($>2\times$ ULN) or clinical jaundice in the absence of cholestasis or other causes of hyperbilirubinemia is considered to be an indicator of severe liver injury (as defined by Hy's Law). Therefore, investigators must report as an adverse event the occurrence of either of the following:

- Treatment-emergent ALT or AST $>3\times$ baseline value in combination with total bilirubin $>2\times$ ULN (of which $\geq 35\%$ is direct bilirubin)
- Treatment-emergent ALT or AST $>3\times$ baseline value in combination with clinical jaundice

The most appropriate diagnosis or (if a diagnosis cannot be established) the abnormal laboratory values should be recorded on the Adverse Event eCRF (see Section 5.3.5.2) and reported to the Sponsor immediately (i.e., no more than 24 hours after learning of the event), either as a serious adverse event or an adverse event of special interest (see Section 5.4.2).

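### The SAP's Hy's Law listing ties ALT/AST only to each participant's own baseline, so it can leave out participants with raised baselines whose transaminases and bilirubin rise together

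*SAP*

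**What the plan says.** SAP 4.3.3.1 defines the listing in one sentence. The transaminase limb reads "Potential Hy's law patients will be listed based on the laboratory data only: treatment-emergent elevated ALT or AST ($>3 \times$ baseline value", and the bilirubin limb follows: "in combination with elevated total bilirubin ($>2 \times$ upper limit of normal [ULN". SAP 4.1 takes baseline as the last value before the first dose.

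Protocol 5.3.5.7 uses the same transaminase multiple for investigator reporting, with a further condition on bilirubin: "Treatment-emergent ALT or AST $>3\times$ baseline value in combination with total bilirubin $>2\times$ ULN (of which $\geq 35\%$ is direct bilirubin". An alternative form replaces the bilirubin limb with clinical jaundice. The section's opening describes the combination "in the absence of cholestasis or other causes of hyperbilirubinemia is considered to be an indicator of severe liver injury". The liver entry in the list of adverse events of special interest (AESIs) in Protocol 5.2.3 refers to this section.

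Entry limits are in Protocol 4.1.1.1. ALT and AST may be up to 2.5×ULN. One exception begins "Participants with documented liver metastases: AST and ALT" and allows 5×ULN. Another begins "Participants with known Gilbert disease: total bilirubin" and allows 3×ULN. No lower bound is set.

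The scheduled chemistry panel in Protocol 4.5.6 ends with "total protein, albumin, phosphate, calcium, total bilirubin, ALP, ALT, AST, and LDH". Direct bilirubin is not in it.

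**The concern.** The rule mixes two scales. Bilirubin is judged against the laboratory's upper limit, and ALT/AST against the participant's own starting value. The plan deliberately admits people whose starting value is already raised, so the absolute ALT/AST level needed for listing rises with it. The participants most affected are those who enter with abnormal liver tests.

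Immune-mediated hepatitis is a named risk in Protocol 5.1.1. The listing is the one planned laboratory output that puts a transaminase and bilirubin together in the same participant. Graded summaries and shift tables describe laboratory results without being specified to show that two tests rose together. The AESI tables could hold combined cases, but the AESI definition uses the same baseline multiple. At stake is which participants a safety reader is prompted to look at.

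**Working it through.** The plan gives no derived figure to reproduce, because this is a threshold definition.

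**Inputs.** Transaminase multiple 3 × baseline and bilirubin limit 2×ULN (SAP 4.3.3.1). Entry limits 2.5×ULN and 5×ULN (Protocol 4.1.1.1). About 175 participants, up to one-third with Stage IV disease (SAP 2.2).

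**Step 1: the effective trigger.** With baseline *b* in ULN units, the listing needs ALT or AST above 3*b* × ULN.

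| Baseline (×ULN) | Needed for listing (×ULN) | Relative to a baseline at ULN |
|---|---|---|
| 1.0 | > 3 × 1.0 = 3.0 | 1 |
| 2.0 | > 3 × 2.0 = 6.0 | 2 |
| 2.5 (general limit) | > 3 × 2.5 = 7.5 | 7.5 / 3 = 2.5 |
| 5.0 (liver metastases) | > 3 × 5.0 = 15.0 | 15 / 3 = 5 |

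**Step 2: example cases.** These values are illustrative. Baseline bilirubin is taken as 2×ULN or less. The second flag is the one proposed under the fix.

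| ALT, baseline to worst (×ULN) | Bilirubin (×ULN) | Multiple of baseline | Listed now | Second flag |
|---|---|---|---|---|
| 2.4 to 7 | 3 | 7 / 2.4 = 2.92 | No | Yes |
| 2.5 to 7 | 4 | 7 / 2.5 = 2.8 | No | Yes |
| 5 to 14 | 4 | 14 / 5 = 2.8 | No | Yes (14 > 5) |
| 5 to 5 | 2.5 | 5 / 5 = 1 | No | No (no rise) |
| 1 to 3.5 | 2.5 | 3.5 / 1 = 3.5 | Yes | Yes |

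At a baseline of exactly 1×ULN the two ALT/AST thresholds coincide. The first three rows are the omissions. The fourth shows why a bare 3×ULN rule needs a guard: without the rise condition, a stable participant at 5×ULN would be listed as soon as bilirubin passed 2×ULN.

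**Step 3: the low end.** The trigger falls to ULN when 3*b* = 1, that is, at a baseline of one-third of ULN. At an assumed baseline of 0.3×ULN it is 0.9×ULN. Whether such a value qualifies depends on the word *elevated* (see the objection).

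**Step 4: who can be affected.** A baseline near 2.5×ULN is possible in any participant. The 5×ULN limit needs liver metastases and so arises only in Stage IV. That is some part of about 175 / 3 = 58 participants if the one-third share is kept; the plan allows it to increase. The documents give no baseline ALT/AST distribution, so no count follows.

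**The case against.** **Other routes capture liver injury.** A reader might infer that the plan would miss serious liver injury altogether. The documents do not support that. SAP 4.3.3.1 also commits to CTCAE-graded data and shift tables to the worst value. Protocol 5.3.5.5 makes a laboratory result a reportable adverse event if it changes study treatment, needs intervention or is clinically significant. Serious events carry the same 24-hour reporting as AESIs, and Appendix 9 has its own hepatic rows. This stands: the gap is in this listing and in the AESI criterion that shares its multiple, not in safety reporting as a whole.

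**The low-baseline problem may not exist.** A reader might infer that the listing flags normal transaminases. The SAP says *elevated*, and on a natural reading 0.9×ULN is not elevated. The bracket could equally be read as the definition of the word. That is an ambiguity to settle, not an established fault, and such a participant would also need bilirubin above 2×ULN. Any large fold-range that starts from a 0.3×ULN baseline rests on a value found nowhere in the documents.

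**Leaving out the direct-bilirubin condition looks like an error.** It makes a listing of potential cases more inclusive, and the scheduled panel could not supply the fraction. A participant with Gilbert disease may already be over the bilirubin limit at entry, but still needs the ALT/AST rise to be listed.

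**A baseline reference can be deliberate.** It avoids listing people whose raised values are stable. That is a fair reason to keep it, although the documents give no rationale and apply it to everyone. It does not explain why it is the only flag.

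**The two documents agree on the multiple.** They do, so this is not a contradiction on the main point.

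**Conclusion.** The point holds in a limited form. At the entry limits the listing requires ALT/AST above 7.5×ULN, or above 15×ULN with liver metastases. That is 2.5 and 5 times the level needed from a baseline at ULN. It can therefore omit participants whose transaminases and bilirubin rise together from a raised start, and no other planned laboratory output is specified to bring the two tests together.

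The arithmetic is exact for a given baseline. The entry limits bind the qualifying screening value, while the SAP baseline is the last pre-dose value and may come from a later sample, so they are an approximate ceiling. How many participants would be affected is unknown. Calling the first three example cases omissions takes 3×ULN as a useful display level, which is an assumption made here.

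A reader might go further and conclude that the AESI trigger must be rewritten. The documents do not settle that, and it is a matter for the sponsor. This is a cheap improvement to a descriptive listing; it does not touch the preference analysis.

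**What to change.** In SAP 4.3.3.1:

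- Keep the flag for more than 3 × baseline with total bilirubin above 2×ULN.
- Add a second flag: post-baseline ALT or AST above 3×ULN with total bilirubin above 2×ULN. If ALT, AST or bilirubin was already over its limit at baseline, require a rise above baseline for that test.
- State that *elevated* means above ULN.
- For each listed participant, print baseline, ×ULN, ×baseline, which flag was met, and known Gilbert disease.

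This takes a wording change and one listing program. ALT, AST and total bilirubin are in the scheduled panel, and local laboratory ranges are collected (Protocol 9.5). The cost is a slightly longer listing. Any rise above a raised baseline would qualify, so some small changes will be listed; the printed baselines let a reader discount them.

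Separately, the sponsor should reconcile the SAP listing with Protocol 5.3.5.7, including the direct-bilirubin condition that the scheduled panel does not supply. Any change to the protocol's reporting trigger would be an amendment needing approval under Protocol 9.7, so the SAP change should not wait for it.

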4.3.3.2 Vital Signs

Vital signs, changes in vital signs and shift table from baseline versus worst post-baseline as well as ECOG performance status will be summarized by treatment sequence over time and overall.

4.3.3.3 ECGs

Changes from baseline on ECG parameters and results of on-study ECGs will be summarized by treatment sequence and overall.

4.4 OTHER ANALYSES

When applicable, exploratory analysis will be done on all patients and separately among participants with early-stage NSCLC and chemotherapy-naive participants with Stage IV NSCLC.

4.4.1 Summaries of Conduct of Study

Enrolment, eligibility violations and participant disposition will be summarized for participants by randomized treatment arm. Reasons for participant's study treatment discontinuation and participant's reasons for study discontinuation will be listed by participant and summarized. Major protocol deviations will be summarized and listed.

Median follow-up on treatment and on study, estimated with corresponding 95% CI by the reverse Kaplan-Meier approach, will be presented for all patients.

Follow-up time on study is calculated from the date of the Cycle 1 visit. Patients who died on study are censored at the time of death. Other patients are considered to have been followed until the date of study completion or discontinuation. If neither of those dates is available, the date of the last recorded visit will be used.

Follow-up time on treatment is calculated from the date of the first study treatment to the date of last study treatment +21 days, date of death, or date of study discontinuation, whichever occurs first.

All analyses will be performed on the FAS.

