Atezolizumab will be administered on Day 1 of each 21-day cycle. Participants will receive atezolizumab according to their assigned route of administration (i.e., SC or IV) for the first three treatment cycles. At Cycle 4, participants will cross-over and receive atezolizumab administered according to the alternative route of administration for Cycles 4–6. This period of 3+3 cycles in both treatment arms constitutes the study Treatment Cross-over Period.

After Cycle 6, participants will select how they would like atezolizumab to be administered (SC or IV) for the Treatment Continuation Period. The Treatment Continuation Period will continue until Cycle 16 for participants with early-stage NSCLC or until loss of clinical benefit, as determined by the investigator according to local standard of care, for patients with advanced NSCLC.

Participants will undergo an End of Treatment Visit within 30 days after completing study treatment and will enter *the safety follow-up period*. *Safety follow-up should occur approximately 90 days after the last dose of study treatment. Thereafter, participants will be contacted for survival status and to collect details of new anti-cancer therapy, if any.*

Participant preference will be assessed based on the PPQ (administered following treatment administration on Day 1, Cycle 6 of the Treatment Cross-over Period). Treatment satisfaction will be assessed based on the TASQ (administered following treatment administration on Day 1 of Cycles 3 and 6 of the Treatment Cross-over Period). Healthcare professionals will record their perception of time/resource use and convenience of treatment administration completing the HCPQs. Perception of time/resource use will be captured during the Treatment Cross-over Period and perception of convenience will be captured after administration of each participant's treatment Cycle 6. Health-related quality of life will be assessed using the EORTC QLQ-C30 completed during the Treatment Cross-over Period (at Cycle 1, Cycle 3, and Cycle 6), during the Treatment Continuation Period (at Cycle 7, Cycle 10, Cycle 13, and Cycle 16), and at the end of study treatment visit. Health utilities will be collected using the EQ-5D-5L questionnaire at the same time points as the EORTC QLQ-C30. The study questionnaires are provided in [Appendix 4](#), [Appendix 5](#), and [Appendix 6](#).

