4.1 GENERAL CONSIDERATIONS

The primary analysis will take place when all study participants have completed their last study treatment administration in the Treatment Cross-over Period. Summaries of secondary study endpoints, including PK and ADA measurements, participant-reported TASQ and EORTC QLQ-C30 responses, selection of treatment administration method for the Treatment Continuation Period, HCP reported HCPQ responses, and safety endpoints will be included in the primary analysis, based on all data up to the clinical cut-off date.

The final study analysis that includes all secondary endpoints including all questionnaires, PK, ADA, and safety endpoints will be conducted after the end of the study (i.e., when all patients have received 16 cycles of atezolizumab or discontinued study treatment).

Summaries of participants' preference, analysis of PROs, including the primary endpoint, HCP reported outcomes and clinical benefit, as well as sensitivity analysis for preference and satisfaction, will be based on the FAS, according to the treatment sequence assigned.

All safety analyses will be performed in the safety-evaluable population, unless otherwise specified. Participants will be analyzed according to the treatment they actually received. In case of protocol deviations leading to a treatment sequence with more than one treatment switch, participants will be analyzed according to the treatment sequence assigned.

Continuous variables will be summarized by the mean, standard deviation, median and range (minimum and maximum). Categorical variables will be summarized by number/percentage of participants.

Unless otherwise stated, baseline values are the last available data obtained prior to the patient receiving the first dose of study treatment (or at screening, for patients who were not treated).

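### SAP 4.4.1 ends the two follow-up times by inconsistent rules, so at the primary analysis a participant still being dosed can have longer follow-up on treatment than on study

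*SAP*

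**What the plan says.** SAP 4.4.1 commits to both figures: "Median follow-up on treatment and on study, estimated with corresponding 95% CI by the reverse Kaplan-Meier approach, will be presented for all patients". Protocol 6.2 names the same two medians and gives no date rule.

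- **On study, start.** "Follow-up time on study is calculated from the date of the Cycle 1 visit".
- **On study, end.** "Patients who died on study are censored at the time of death". Everyone else runs to study completion or discontinuation. "If neither of those dates is available, the date of the last recorded visit will be used".
- **On treatment.** "Follow-up time on treatment is calculated from the date of the first study treatment to the date of last study treatment +21 days", cut short only by death "or date of study discontinuation, whichever occurs first".

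Neither rule names the clinical cut-off date. SAP 4.1 says that the secondary and safety summaries at the primary analysis are "based on all data up to the clinical cut-off date". That analysis is triggered once every participant has had the last cross-over dose. Under Protocol 3.1.1, treatment then continues to Cycle 16 in early-stage disease, or to loss of clinical benefit in Stage IV. After treatment and the 90-day safety contact, "participants will be contacted for survival status and to collect details of new anti-cancer therapy, if any".

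**The concern.** Time on treatment is part of time on study, so it cannot be the longer of the two. At the primary analysis, a participant in the continuation period has no completion or discontinuation date, so the last-visit fallback is the rule that applies. That rule stops the on-study clock at about the last dose, while the treatment rule adds 21 days to the same dose. The added days may lie beyond the data cut-off, and so be time that nobody has observed.

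A second weakness concerns participants who have stopped treatment but are still contacted for survival. Their on-study follow-up depends on what counts as a visit, which the SAP does not define. Two programmers could reasonably report different medians.

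At stake is whether two prespecified descriptive figures, each with a 95% CI, describe the follow-up actually observed.

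**Working it through.** The documents state no follow-up figure, so there is nothing to reproduce. The check applies the rules to dates.

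**Inputs.** Dosing is on Day 1 of 21-day cycles (Protocol 3.1.1), with a window of 3 days either side (Appendix 1). Appendix 1 schedules only Day 1 visits during treatment; Appendix 2 adds one sample on Cycle 1 Day 4. The end-of-treatment visit falls within 30 days of the last dose, and the 90-day contact is labelled a telephone call (Appendix 1).

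**Step 1: who is affected.** On schedule, Cycle 6 Day 1 falls 5 × 21 = 105 days after Cycle 1 Day 1, and Cycle 16 Day 1 falls 15 × 21 = 315 days after it. If the cut-off is the last participant's Cycle 6 dose, an early-stage participant who started less than 315 − 105 = 210 days before that last participant, and has not stopped, has not reached Cycle 16. Stage IV participants have no cycle limit. The fallback will therefore be used often.

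**Step 2: participant still on treatment.** Count days from the first dose. Let D be the last dose, C the cut-off and t = C − D, with the last recorded visit being the last dosing visit.

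- On study = D; on treatment = D + 21; difference = 21 for any t.
- On treatment passes the cut-off by 21 − t. On study stops t days before it.

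| t | On treatment minus on study | Days past cut-off | On study short of cut-off |
|---|---|---|---|
| 0 | 21 | 21 | 0 |
| 7 | 21 | 14 | 7 |
| 10.5 | 21 | 10.5 | 10.5 |
| 20 | 21 | 1 | 20 |
| 21 | 21 | 0 | 21 |

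Example: last dose on day 210, cut-off on day 220. The rules give 210 days on study and 231 on treatment. The participant has been observed for 220.

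**Step 3: participant off treatment, still in survival follow-up.** Last dose on day 42, end-of-treatment visit on day 42 + 30 = 72, cut-off on day 300. On-study follow-up is 72 days if only clinic visits count and 42 + 90 = 132 if the telephone call counts. It is later still if survival contacts count.

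**Step 4: effect on the medians.** In a reverse Kaplan-Meier estimate each survivor's end date is an event time, so these dates enter the median directly. The simulation used 175 participants, a cut-off 105 days after the last Cycle 1, and 60 trials per scenario. These assumptions are not in the documents: accrual over 270, 365 or 450 days; discontinuation hazard 0, 0.05 or 0.08 per month; 0–20% of doses delayed; an extra recorded visit in 0–30% of cycles; 30% of discontinuations ending in death; only clinic visits counted. Mean medians in days for 365-day accrual with no delays or extra visits:

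| Monthly hazard | On study, as written | On treatment, as written | On treatment, capped | On study, run to cut-off |
|---|---|---|---|---|
| 0 | 275 | 296 | 286 | 286 |
| 0.05 | 231 | 243 | 236 | 289 |
| 0.08 | 204 | 213 | 206 | 287 |

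Across all scenarios the on-treatment median is about 4 to 10 days longer than the capped one, and about 4 to 21 days longer than the on-study median as written.

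On schedule, every participant still on treatment shows exactly 21 extra days, and 95–96% run past the cut-off. With delays and extra visits, 73–90% show exactly 21, 92–97% still have longer follow-up on treatment than on study, 84–91% run past the cut-off, and the mean excess is 17–19 days.

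**The case against.** **It is only descriptive.** This stands. The primary result is a preference proportion with a Clopper-Pearson interval (SAP 4.2.2), with no hypothesis test (SAP 2.1). Exposure is summarised separately in SAP 4.3.1, which does not say that it uses these rules.

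**SAP 4.1 already limits the data to the cut-off.** A programmer might truncate on that basis. But the clause governs which data enter. Last dose plus 21 days is calculated from a dose given before the cut-off, so nothing in the text truncates it, and a data cut cannot lengthen on-study time.

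**Both conventions are ordinary.** Crediting a full cycle after the last dose is reasonable, and stopping at the last visit is cautious. Each is defensible alone; together they put the participant-level times in an impossible order.

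**Stronger readings are tempting.** A reader might infer that everyone still on treatment gains exactly 21 days. That fails when a dose is withheld, which Protocol Appendix 9 allows for up to 12 weeks and longer for a steroid taper, or when an unscheduled visit is recorded.

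A reader might also infer that the on-study median is understated by as much as 41%, or that the two medians usually come out reversed. One simulation does give this: 12-month accrual, 28% loss by Cycle 6, no deaths or withdrawals. Its on-study medians are about 167 days (clinic visits only), 194 (counting the 90-day call) and 259 (survival contacts every 90 days), against 285 if follow-up runs to the cut-off. The shortfalls are (285 − 167)/285 = 41%, (285 − 194)/285 = 32% and (285 − 259)/285 = 9%. Reversal occurs in about 55% of trials if only clinic visits count, about 1% if the call counts, and about 0% with regular survival contacts. At 3% drop-out per cycle the clinic-only figure is 72–75%, and 18% if the call counts. If half of those who drop out leave the study, the 285 falls to about 228 and the largest shortfall to about 27%.

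The SAP does not restrict visits to clinic attendance and does not make the cut-off the correct end of on-study follow-up. The planned 28% is for missing preference assessments, not treatment drop-out. The documents therefore support none of these percentages as an expected size.

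**Conclusion.** The point holds as an inconsistency between two derived dates, not as two directly opposed statements. Read literally at the primary analysis, SAP 4.4.1 typically makes on-treatment follow-up up to 21 days longer than on-study follow-up for a participant still being dosed. The gap is exactly 21 days when the last recorded visit is the last dosing visit. On-treatment follow-up passes the cut-off whenever the last dose was less than 21 days before it. This participant-level result needs only the text and the visit schedule.

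The effect on the medians does rest on assumptions: about 4 to 10 days too long on treatment in the scenarios run. For participants off treatment, on-study follow-up may be understated, but the size cannot be fixed from the documents. Nothing inferential changes: the preference estimate, its interval and the sample size are untouched. The gap could recur at the final analysis for Stage IV participants still being dosed, because the treatment rule is capped at study discontinuation and not at study completion.

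**What to change.** In SAP 4.4.1:

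- End on-treatment follow-up at the earliest of last dose plus 21 days, death, study discontinuation or the clinical cut-off date of the analysis.
- For participants with no completion or discontinuation date, end on-study follow-up at the later of two dates: the last date known to be in follow-up (visits, dosing and survival contacts, up to the cut-off) and the end of on-treatment follow-up as capped above. Time on study is then never shorter than time on treatment. Using the cut-off date for all participants still in the study also achieves this. Choose one and state it.

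In the day-210 example, on treatment becomes min(231, 220) = 220 and on study becomes max(210, 220) = 220. The cost is two phrases in the SAP and one programming change, with no new data.
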